7.2.12 Management of Conflicts with Physician-Ordered Care

All participants will receive standard care as ordered by their personal, treating physician. Efforts will be made to integrate the REHAB-HF intervention into the standard of care ordered by the treating provider. In the event of conflict between standard care and the REHAB-HF intervention assignment, the study protocol will yield to individual, physician-ordered standard care.

7.3 Intercurrent Illness and Interruption to Study Intervention

Interruptions to the study intervention, including illness and hospitalization, are anticipated. Although this is an intention-to-treat protocol, to help ensure each participant has a reasonable opportunity to complete the study intervention (defined as completing at least 30 outpatient sessions) and that the physical performance outcome measures reflect the intended intervention of this study, limited extensions of the study intervention are included in the study protocol. Participants who suffer an illness, hospitalization or other complications that interferes with participating in the study intervention will resume the intervention once medically stable. Participants will have up to 4 additional weeks beyond the initially planned 12 weeks to attempt to complete the multi-domain intervention.

In addition, if a participant is acutely ill or hospitalized within 2 weeks of the anticipated date of the final 3-month visit, the visit will be delayed for up to 2 weeks to allow for up to 6 additional rehabilitation and exercise sessions. Similarly, the final 3-month visit for those in the attention control arm will also be delayed for up to 2 weeks in the event of acute illness or hospitalization within 2 weeks of the date of the visit.

7.4 Monitoring of Exercise and Rehabilitation

The details regarding the number of rehabilitation sessions attended as well as key markers of adherence to the exercise prescription and progression will be recorded and entered into the secure database by the study personnel supervising the rehabilitation and exercise training. In addition, participants in both the study intervention arm and the attention control arm will keep a diary of any exercise performed or any usual care rehabilitation received.

Participants in the rehabilitation intervention arm will be issued a pedometer to promote adherence to home exercise and activity goals.

Participant adherence with both exercise diary entries and wearing of a pedometer will be encouraged throughout the study during follow-up visits and phone calls.

8. Retention and Treatment Fidelity

8.1 Overview

In order for the REHAB-HF study to be successful, we will implement proactive procedures to insure that we (1) retain participants in accord with the intent-to-treat principle, (2) deliver the REHAB-HF intervention safely and effectively as outlined in the protocol, and (3) maximize adherence to intervention.

8.2 Retention

8.2.1 Adherence Screening and Behavioral Agreement

Retaining participants in the study will begin prior to enrollment. Following informed consent, a brief adherence screening tool and behavioral agreement will be completed. The adherence screening tool explains the basic commitments of the rehabilitation intervention and asks the participant to rate the degree of: 1) conflicts from other commitments/personal issues interfering with the intervention, 2) difficulty in obtaining transportation, 3) how they think their primary physician would feel about the study intervention, and 4) their confidence in being able to carry out the intervention. The behavioral agreement is a document to be signed by the participant detailing the requirements of REHAB-HF and indicating the participant's willingness to complete the requirements of either treatment arm of the intervention once randomized.

This process will not only allow us to identify adherence risks, but along with informed consent, it will also be used as a mechanism to give participants an in-depth understanding of REHAB-HF and enable us to collect information to assist in the tailoring of treatment.

The study team at each site will carefully discuss the information gleaned from these assessments to make a final determination on behavioral suitability for REHAB-HF.

8.2.2 Retention Promotion Efforts

To promote retention, the following steps will be followed: 1) provision of a clear schedule of all visits, reminders, same-day phone calls for any missed visits, involvement of family and caregivers, and sharing of test results and intervention progress, if applicable; 2) free parking for study visits and intervention sessions; 3) transportation to study visits and intervention sessions as needed for participants of low socioeconomic status; and 4) required in-person contact within the first 2 weeks following discharge, achieved through intervention sessions, home visit, or meeting at a usual care clinic visit or if necessary, a scheduled clinic visit.

8.2.3 Retention for Study Visits

Algorithms are developed to address non-attendance to study visits. These involve procedures (discussed below) that facilitate documentation of these events and how best to rectify the problem. The following procedures will be implemented (as appropriate in each site) to carefully document and monitor missed study visits:

- Preparing for the next visit at the end of each current visit by making the appointment and giving instructions for the next visit
- Rescheduling the visit within the same window, if possible. Examinations that fall
 outside of the target window remain important and are used in all analyses. These
 examinations are assigned to whichever target visit would be the closest in time. If it
 becomes clear that a visit corresponding to a particular set of forms (e.g. a 3-month
 visit) is not completed, a Missed Visit form is filled out

The following guidelines are implemented to promote adherence to study visits:

- Fostering personal relationships between participants and individual members of the staff
- Insuring that the clinic environment is warm and pleasant, and oriented to the comfort of the patient
- Using easily accessible clinic locations, providing transportation when necessary, and convenient clinic hours all serve to facilitate study adherence
- Keeping total clinic visit time to a minimum. If waiting is necessary, the situation is
 explained to the participant and, if possible, an offer is made for the participant to see
 another staff member, or to reschedule the visit
- Appointment reminders are used to prompt participants to attend clinic visits

8.2.4 Monitoring Recruitment and Retention

The study investigators, including [name], consultant for retention and adherence, will routinely monitor screening and recruitment yields, and compare these to preset gender and ethnic minority benchmarks for each site. If sites encounter difficulties with recruitment or retention, the investigators will partner with the site in question to establish specific steps to assist in resolving the problem encountered.

8.2.5 Retention and Efforts to Maintain Contact with Inactive Participants Retention is promoted by:

- Examining and attempting to remove barriers (e.g., by addressing parking and other transportation issues, adjusting clinic hours).
- Incorporating a variety of methods to promote contact with all participants and provide social support for all participants.
- Ensuring that participants' concerns are identified and addressed before they express a desire to reduce their involvement in the study.

REHAB-HF has the goal of maintaining some form of contact (e.g., phone, e-mail) with participants who are unable to continue full engagement in the study and to foster some form of continued involvement (e.g., even an agreement to allow future contact) with participants who are inactive in the study. Priority is given to attending assessment visits.

8.3 Treatment Fidelity: Delivering the Physical Activity Intervention as Detailed in the

Critical to the success of REHAB-HF is insuring fidelity of the intervention. There are 3 steps taken to address this facet of study conduct.

- 1. Prior to study launch, all intervention personnel will participate in on-site training sessions. Training materials will include videos, handouts, and case presentations, as well as hands-on demonstrations for each site. The training will be led by [name], overall trial intervention leader, who will review, critique, and provide feedback to the interventionists.
- 2. The intervention will be carried out in a standardized manner across treatment sites. To facilitate this, the intervention protocol contains a standardized protocol for guiding exercise prescription (section 7.3.2) and exercise progression (section 7.3.5), the two most critical pieces to ensure consistent implementation.
- 3. An intervention committee will regularly review intervention adherence, progression, and fidelity. This committee will comprise of [name] and the intervention supervisors from each site along with [name], as needed. This committee will regularly review real-time reports generated from the study database to track attendance and progression on key measures in each domain (such as walking distance, sit-to-stand level achieved). Bi-weekly teleconferences, including the interventionists, will be used to discuss the progress of individual participants, the performance of interventionists and sites, and to troubleshoot any potential barriers to attendance or progression that may arise.

9. Study Participant Follow-up

9.1 Follow up schedule

All baseline measures (see Table 2) will be collected during the index hospitalization. Follow up visits will occur 4 weeks ± 3 days and 12 weeks ± 10 days (unless intervention is extended, see section 7.3) from the day of discharge from the index hospitalization. These visits will include a brief history and physical and collection of study measures (see Table 2). Historical information will include heart failure symptoms, NYHA class, current medications, the results of any intervening cardiac studies (echocardiogram, stress tests, etc.), and the occurrence of any clinical events. The focused physical examination will include evaluation of the lungs, heart, and periphery. During these visits, the participants will also complete health status and quality of life measures as well as follow-up measures of physical function as detailed in Table 2 below. To promote retention, all participants will receive in-person contact within the first 2 weeks following discharge, achieved through intervention sessions, home visit, usual care clinic visit, or a scheduled clinic visit. In addition to the follow up visits, participants will receive a scheduled phone call at the end of months 2, 4, 5, and 6 to evaluate clinical status and for follow-up on adherence to the maintenance phase. Additional telephone contact will be made with the attention control group participants (see section 7.1). Telephone contact will also be maintained with participants unable or unwilling to attend the clinic visits. In some instances, participants unable to attend these visits may receive a home visit to collect important end points.

Table 2: Collection of Outcome Measures

	Index Hospitalization (Baseline)	1 Month (Visit)	2 Months (phone call)	3 Months (Visit)	4, 5, & 6 Months (phone call)
6MWT	X	X		X	
SPPB	X	X		X	
Grip	X	Х		Х	
Biomarkers	X			X	
Bioenergetic Profiling	Х			Х	

KCCQ	X	Х		Х	
SF-12	Х	Х		Х	
EQ-5D-5L	Х	X		X	X (6M only)
GDS-15	Х			Х	
LOT	Х			Х	
MoCA	Х			Х	
Clinical	Х	Х	Х	Х	Х
Events	^	^	^	^	^
Medications	Х	Х	Х	Х	Х
Review	Λ	^		X	^
Medical					
Resource		X	X	X	X
Use					

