7.1 Attention Control

Participants randomized to the attention control arm will be notified immediately, and will follow standard care as ordered by their individual, treating physician. Importantly, to reduce the potential for bias from greater attention and surveillance in the rehabilitation intervention group, participants in the attention control group will receive at least bi-weekly contact from study personnel during the first 3 months following the index hospitalization. This contact will be provided as a combination of telephone calls and specified study visits. Specifically, contact will be made with study visits at weeks 4 and 12 and with telephone calls at weeks 2, 6, 8, and 10. Further, in-person contact will be made within the first 2 weeks following discharge for the purposes of retention (section 8.2.2). Consistent with the rehabilitation intervention group, telephone contact will also be made at weeks 14, 16, 20, and 24. Information regarding symptoms, HF transitional management program use, medical compliance, activity level, rehabilitation received, medical resource utilization, and clinical events will be collected at each of these encounters.

Participants in the attention control arm will not receive any specific rehabilitation recommendations or exercise prescription from study personnel. They may, however, receive any physical or occupational therapy deemed appropriate by their usual clinical care providers, both during the hospitalization and as outpatients.

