7.2.8 Exercise Safety

During each exercise session, participants will sign an attendance sheet and log any health-related problems or symptoms they are experiencing. These sheets will be reviewed by intervention staff before initiating physical activity. Should a participant report a significant change in health status (see safety parameters below) before or during exercise, a study physician onsite or the participant's primary doctor should be consulted prior to exercise participation. Vital signs, including heart rate, blood pressure and pulse oximetery will be recorded at the beginning and conclusion of each session. Routine assessment of heart rate during the exercise session will also be used to enhance exercise safety. Exercising blood pressure and pulse oximetery will be monitored on a symptom-driven basis as needed during the trial to ensure participant safety.

For participants who meet any of the safety parameters listed below, the following steps and additional monitoring procedures will be conducted:

- Exercise training sessions will be stopped
- The participant will subsequently be re-evaluated for medical contraindications to exercise
- Exercise intensity levels will be re-assessed and modified as needed

Safety Parameters

- Resting blood pressure systolic > 200 mm Hg or diastolic > 100 mm Hg
- Resting blood pressure systolic < 80 mm Hg
- Resting blood pressure systolic between 80 and 89 mm Hg with associated or uncertain symptoms of lightheadedness or dizziness

- Resting heart rate >120 beats/min or < 40 beats/min
- Increase in heart rate ≥90% of age predicted maximum during exercise
- Oxygen saturation < 90% on room air
- Unusual or severe shortness of breath
- Chest pain including chest discomfort or pressure, left arm pain, report of indigestion or stomach discomfort
- Palpitations
- Severe light headedness, dizziness or feeling about to faint
- A physical activity session had to be discontinued because of other symptoms excluding musculoskeletal symptoms (e.g. knees, ankles, hips) reported by the participant
- Decrease in diastolic blood pressure ≥20 mmHg during exercise
- Increase in systolic blood pressure to ≥250 mmHg or in diastolic blood pressure to ≥115 mmHg during exercise
- Decrease in oxygen saturation to <88% on room air during exercise

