13.1 Adverse Events (AE) and Serious Adverse Events (SAE)

The following standard definitions of an adverse event and a serious adverse event are based on NHLBI policy as follows.

1. Adverse event (experience):

Any untoward medical occurrences in participants will be captured, regardless of causal relationship with the intervention and procedures. An AE can therefore be any unfavorable and

unintended sign (including an abnormal laboratory finding), symptoms, or disease temporally associated with the investigational intervention, whether or not considered related to the investigational intervention.

2. Serious adverse event (experience) (SAE):

Any untoward medical occurrences that may result in any of the following outcomes:

- Death
- Is life-threatening
- Requires inpatient hospitalization or prolongation of existing hospitalization
- Results in persistent or significant disability/incapacity
- Is a congenital anomaly/birth defect
- Important medical event that may not result in death, be life-threatening, or require
 hospitalization may be considered a serious adverse event when, based upon
 appropriate medical judgment, it may jeopardize the patient or participant and may
 require medical or surgical intervention to prevent one of the outcomes listed above

Disability is defined as a substantial disruption of a person's ability to conduct normal life's functions (Federal Code of Regulations 21 CFR 312.32)

For the purpose of the REHAB-HF study, the following AE's and SAE's will be reported to the DSMB: death, hospitalization, hospitalization/observation unit stay lasting less than 24 hours, emergency room visit, urgent clinic visits, and adverse events occurring while participant performing the REHAB-HF intervention (including angina, syncope/presyncope, palpitations, symptomatic hypoglycemia and/or falls). All cardiovascular events (including worsening heart failure, acute coronary syndrome, arrhythmia, and stroke) will be collected and reported to the DSMB. For the purpose of this protocol, hospitalizations will be identified as planned or not planned. We will not be collecting specific information on congenital anomalies. At the end of the study or at death, an attempt will be made to ascertain if any permanent disabilities occurred related to the intervention.

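### In weeks 0-12 controls have six scheduled event and resource-use inquiries against three in the intervention arm, which alone has session logs: falls and record-poor resource use risk differential ascertainment of unknown direction

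*Combined protocol and SAP*

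**What the plan says.** Section 7.1 sets the control schedule. It promises that "participants in the attention control group will receive at least bi-weekly contact from study personnel during the first 3 months following the index hospitalization" and then specifies that "contact will be made with study visits at weeks 4 and 12 and with telephone calls at weeks 2, 6, 8, and 10". It lists what is gathered, ending: "medical resource utilization, and clinical events will be collected at each of these encounters". The stated aim is to offset the closer observation that the intervention arm receives.

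Section 9.1 and Table 2 set the schedule for everyone: visits at weeks 4 and 12 and calls at the end of months 2, 4, 5 and 6, each with clinical events and resource use. Section 9.1 then says: "Additional telephone contact will be made with the attention control group participants (see section 7.1". No matching extra inquiry is scheduled for the intervention arm.

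After week 12 the sections disagree. Section 7.1 says: "Consistent with the rehabilitation intervention group, telephone contact will also be made at weeks 14, 16, 20, and 24". Sections 7.2.11 and 9.1 list only months 4, 5 and 6, with no week-14 call.

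The intervention arm has three outpatient sessions a week. Section 7.2.8 says that at each one "participants will sign an attendance sheet and log any health-related problems or symptoms they are experiencing". Section 13.1 sends the DSMB "adverse events occurring while participant performing the REHAB-HF intervention (including angina, syncope/presyncope, palpitations, symptomatic hypoglycemia and/or falls".

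Clinical events come from interviews and medical records review (section 10.6). Resource use comes from self-report and caregiver interview, supplemented by records (section 11.1).

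**The concern.** The control calls balance the amount of contact. They do not balance the event question. Controls are asked about clinical events and resource use every two weeks for 12 weeks. The intervention arm is asked on a four-week cycle, and its session log is a different instrument: it records problems that the participant has at that moment. The protocol does not say that sessions ask about falls, visits or care since the last contact. Section 13 collects falls at all visits without saying whether a session is a visit.

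Two mechanisms then act in opposite directions. A longer recall gap tends to lose events in the intervention arm. Logs and direct observation tend to find events there that would go unreported in control.

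Falls are the most exposed outcome: they are a listed exploratory parameter, many leave no record, and falls during sessions can be seen in one arm only. Outpatient resource use feeds the six-month cost comparison (section 11.4) and the payment proposals (section 11.6). Section 14.1 applies methods like those for the main outcomes to the exploratory parameters. It has no common ascertainment window, no source flag and no sensitivity analysis for this.

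**Working it through.** **Step 1: count the scheduled inquiries.** Sections 7.1, 7.2.11 and 9.1 and Table 2 supply the inputs. Months are converted at 4 weeks each, as the protocol does when it calls the week-4 and week-12 visits the 1-month and 3-month visits.

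| Period | Control | Intervention |
|---|---|---|
| Weeks 0-12 | 2, 4, 6, 8, 10, 12 = 6 | 4, 8, 12 = 3 |
| Weeks 13-24 | 14, 16, 20, 24 = 4 | 16, 20, 24 = 3 (sections 7.2.11, 9.1), or 4 with week 14 (section 7.1) |
| Total | 10 | 6 or 7 |

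The gap is 2 weeks against 4 in weeks 0-12. From week 16 both arms are on 4-week gaps. The intervention arm also has up to 3 x 12 = 36 outpatient sessions with a log. I left out the in-person retention contact in the first two weeks, which both arms have.

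**Step 2: how far could this move a rate ratio?** The documents give no recall or capture rates, so these inputs are assumptions:

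- constant event rate and no true treatment effect;
- exponential forgetting at rate L per week, from 0.02 to 0.20;
- a share q of the events that the intervention arm would otherwise forget in weeks 0-12 is recovered through sessions.

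The share of events captured over a gap of T weeks is c(T) = (1 - exp(-L x T)) / (L x T). The apparent intervention/control ratio in weeks 0-12 is [c(4) + q x (1 - c(4))] / c(2).

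With L = 0.20:

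- c(2) = (1 - 0.6703)/0.4 = 0.824 and c(4) = (1 - 0.4493)/0.8 = 0.688.
- q = 0: 0.688/0.824 = 0.835.
- q = 0.5: (0.688 + 0.5 x 0.312)/0.824 = 1.024.
- q = 1: 1/0.824 = 1.213.

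| L | c(2) | c(4) | q = 0 | q = 0.5 | q = 1 |
|---|---|---|---|---|---|
| 0.02 | 0.980 | 0.961 | 0.980 | 1.000 | 1.020 |
| 0.05 | 0.952 | 0.906 | 0.952 | 1.002 | 1.051 |
| 0.10 | 0.906 | 0.824 | 0.909 | 1.006 | 1.103 |
| 0.20 | 0.824 | 0.688 | 0.835 | 1.024 | 1.213 |

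The ratio crosses 1 when q = (c(2) - c(4))/(1 - c(4)). That is 0.019/0.039 = 0.49 at L = 0.02 and 0.136/0.312 = 0.44 at L = 0.20. So the sign depends on whether sessions pick up more or less than a little under half of what would otherwise be forgotten, and the protocol says nothing that settles this.

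Over weeks 0-24, across both readings of the week-14 call, the ranges are 0.88 to 0.99 (q = 0), 0.98 to 1.01 (q = 0.5) and 1.01 to 1.11 (q = 1).

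**The case against.** The strongest reply is that the asymmetry is deliberate. Section 7.1 introduces the two-weekly control contact to counter bias from closer observation of the intervention arm. With sessions three days a week, that arm is hardly unobserved. If sessions recover about half of the otherwise forgotten events, the two mechanisms nearly cancel. Records review covers all clinical events in section 10.6 and supplements resource use.

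Much of this stands, and it rules out several stronger readings that a reader might infer:

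- **That the comparisons are biased.** The documents fix neither the sign nor the size, and no net bias is a plausible result. A single pair of assumed capture rates would give a single figure, but the documents supply no such rates.
- **That controls are asked twice as often throughout.** This holds for weeks 0-12 only. Later the schedules match or differ by one call.
- **That short emergency department and urgent visits are self-reported efficacy endpoints.** They are not among the efficacy parameters in sections 2.3 or 12.3, and records review applies to them. They matter for DSMB reporting and as cost inputs.

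What does not stand is that a counterweight of unknown size shows balance. Section 7.3 expects interruptions from illness and hospitalization. A participant who misses sessions may have neither session observation nor inquiries at weeks 2, 6 and 10.

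It can also be argued that an analysis limited to the contacts both arms share (weeks 4, 8, 12, 16, 20 and 24) needs no extra forms. That helps only in part. If each form asks about the time since the last contact, the restriction drops control events reported at weeks 2, 6 and 10 and does not equalise recall.

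**Conclusion.** The point holds as a risk of differential ascertainment of unknown direction, mainly for falls and for outpatient resource use that leaves little record, and mainly in weeks 0-12. The counts (6 against 3, then 10 against 6 or 7 in total) come straight from the protocol. The rate-ratio range of about 0.84 to 1.21 in weeks 0-12 rests wholly on the assumed forgetting rates and session recovery. It shows what the design allows and does not estimate what would happen.

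The primary SPPB outcome is unaffected: blinded assessors measure it at visits common to both arms. Rehospitalizations over 24 hours and other record-verified events are less exposed. The serious events in the interim harm review (section 13.2) would normally leave records. This is a worthwhile, inexpensive improvement that does not threaten the main result. It is best made before data collection, because events that were never asked about cannot be reliably recovered later.

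**What to change.** 1. Use one identical event and resource-use form in both arms at the same weeks. In the intervention arm, add weeks 2, 6 and 10 with the same script, by telephone or at that week's session.
2. Reconcile the week-14 call across sections 7.1, 7.2.11 and 9.1, so that both arms have it or neither does.
3. Record the source of every event: common form, medical record, session log or staff observation.
4. Base the main between-arm comparison of falls and resource use on the common form plus records. A fall during a session that is also reported on the form counts.
5. Add a sensitivity analysis that includes events found only through session logs or observation, and report those events separately as intervention safety data. Simply leaving them out could remove genuine intervention-related falls and understate harm.
6. State in section 13 whether an exercise session counts as a visit for collecting falls.

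The cost is three short forms per intervention participant, or four if week 14 is kept, mostly at sessions already attended, plus a protocol wording change and a little more analysis.
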